6.2. CONCOMITANT MEDICATIONS

With the exception of pre- and post-operative standard of care medications, all medication that the subject has taken 30 days prior to Visit 1 and through Visit 7 or discontinuation from the study will be recorded in the eCRF and the subject chart. The generic name of the drug, dose, route of administration, duration of treatment (including start and stop dates), frequency, indication, and whether or not the medication was taken due to an AE will be recorded for each medication.

6.2.1. Permitted Medications

Medications not specifically excluded in Section 6.2.2 may be taken as necessary. Concomitant treatment with antibiotics at the discretion of the Investigator is allowed (with the exception of besifloxacin). Medications routinely administered and not explicitly prohibited in this protocol used as part of an uncomplicated cataract surgery procedure are allowed. These medications will be collected in the source documentation and are not captured within the eCRF unless there is a change to the standard of care as documented in the source document. Further, the routine medications administered as part of routine cataract surgery are not expected to be associated with treatment for AEs unless otherwise indicated. Note: Any medication administered as part of the routine surgery that is ongoing subsequent to the surgical procedure, should be captured in the eCRF as a concomitant medication.

6.2.2. Medications Not Permitted

Use of the following medications is not allowed during the study and for the timeframes specified:

Within 2 days prior to surgery (Visit 2) and for the duration of the study:

- Ocular NSAIDs
- Systemic NSAIDs with the exception of ≤81 mg/day of acetylsalicylic acid (ASA or aspirin)
- Ocular mast cell stabilizers
- Ocular antihistamines
- Ocular decongestants
- All eye drops (except antibiotic eye drops considered to be included in post cataract surgery standard of care treatment). Note: Besifloxacin Ophthalmic Suspension is not permitted within 2 days prior to the surgery or for the duration of the study.
- Glaucoma medications
- All topical ophthalmic gels or artificial tears

Within 7 days prior to surgery (Visit 2) and for the duration of the study:

Topical eyelash growth medications

Within 14 days prior to surgery (Visit 2) and for the duration of the study:

• Systemic or ocular corticosteroids other than study product (except stable maintenance dose of inhaled or intranasal corticosteroids)

Within 30 days prior to surgery (Visit 2) and for the duration of the study:

- Ocular immunosuppressants (e.g., Restasis[®])
- Systemic immunosuppressants (with the exception of oral corticosteroids less than prednisone 11 mg/day or equivalent)
- Other investigational products

Within 6 months prior to the screening visit (Visit 1), alterations to the dose of the following are disallowed:

- Anticholinergics
- Antidepressants

• Oral corticosteroids (dose must be less than prednisone 11 mg/day or equivalent)

NOTE: Dose must remain stable throughout the course of the study

If using nutraceuticals or multivitamins, subjects may not alter their stable dose throughout the study.

6.3. STUDY PRODUCT USE COMPLIANCE

Compliance will be assessed by comparing study product accountability records with the dosing information recorded daily by the subject. The site will document this comparison along with verification of the numbers of used and unused study product bottles. The numbers of missed doses as assessed at each clinic visit should be documented in the eCRF.

6.4. DRUG ACCOUNTABILITY

Sponsor study monitors or designees will conduct accountability of study product (KPI-121 or placebo). Accountability will be ascertained by performing reconciliation between the amount of drug sent to the site and the amount unused at the time of reconciliation.

Clinical trial materials will be shipped to the investigational sites under sealed conditions. Study product shipment records will be verified by comparing the shipment inventory sheet to the actual quantity of drug received at the site. Accurate records of receipt and disposition of the study product (e.g., dates, quantity, subject number, dose dispensed, returned) must be maintained by the Investigator or his/her designee. Study product will be stored in a secure area with limited access at 15-25°C/59-77°F with upper limit excursions to 30°C /86°F allowed.

At the end of the study, all study materials, including any unused study product (KPI-121 study product or placebo), as well as original containers (even if empty), will be returned to the drug packaging vendor in accordance with sponsor or designee's standard operations procedures (SOPs), following approval by the Sponsor. All returns of study product will be documented. The study monitor or designee will verify drug accountability. All drug accounting procedures must be completed before the study is considered complete.

6.5. MAINTENANCE OF RANDOMIZATION AND PROCEDURE FOR BREAKING THE CODE

The sponsor, the project teams at the designated Contract Research Organizations (CROs), and investigative staff responsible for assessments of study endpoints will be masked to study product assignments. In case of medical emergency, or occurrence of an SAE, the

randomization code may be unmasked and made available to the Investigator, sponsor, and/or other personnel involved in the monitoring or conduct of this study. In the absence of medical need, the randomization code will not be available to the above individuals until after the study is completed and the database is locked.

In the event of a medical need, the Investigator will treat each subject as needed. Since there is no specific antidote to KPI-121, immediate emergency unmasking is not necessary. If the Investigator feels it is necessary to unmask a subject's assignment after an emergency situation, the Investigator may call the medical monitor and notify the sponsor. The study product assignment will be revealed on a subject-by-subject basis with the approval of the medical monitor and sponsor, thus leaving the masking of the remaining subjects intact.

A randomization code will be computer-generated by Kala Pharmaceuticals, Inc. or its designee.

Randomization team members will work independently of other team members at the CRO. Study personnel, study subjects, the sponsor, and project teams at the CROs involved in the study will be masked to study product assignments.

7. ASSESSMENT OF EFFICACY

Efficacy Assessments include the following:

- Slit Lamp Biomicroscopy examination of the following ocular signs of inflammation:
 - Signs of anterior ocular inflammation (i.e., cells; 0-4 Scale and flare; 0-4
 Scale)
- Subject-Rated Ocular Pain Assessment (0-5 Scale)
- Rescue therapy

8. ASSESSMENT OF SAFETY

8.1. SAFETY PARAMETERS

Safety parameters include:

- Assessments of AEs
- Snellen Distance VA by Pinhole Method
- Slit Lamp Biomicroscopy including assessment of the following signs of inflammation: Palpebral conjunctival erythema, corneal edema, hyphema, ciliary flush, bulbar conjunctival injection
- IOP Measurement
- Dilated Ophthalmoscopy

8.2. ADVERSE EVENT DEFINITIONS

Adverse Event (AE): Any untoward medical occurrence associated with the use of an investigational product in humans, whether or not considered drug related.

Adverse Reaction (AR): any AE caused by a drug. Adverse reactions are a subset of all suspected adverse reactions where there is reason to conclude that the drug caused the event.

Suspected Adverse Reaction (SAR):

Any AE for which there is a reasonable possibility that the drug caused the AE. For the purposes of IND safety reporting, "reasonable possibility" means there is evidence to suggest a causal relationship between the drug and the AE. A SAR implies a lesser degree of certainty about causality than adverse reaction, which means any AE caused by a drug.

Unexpected: An AE or SAR is considered "unexpected" if it is not listed in the Investigator's Brochure or is not listed at the specificity or severity that has been observed; or, if an Investigator's Brochure is not required or available, is not consistent with the risk information described in the general investigational plan or elsewhere in the current application.

Life-threatening: An AE or SAR is considered "life-threatening" if, in the view of either the Investigator or sponsor, its occurrence places the patient or subject at immediate risk of death. It does not include an AE or suspected adverse reaction that, had it occurred in a more severe form, might have caused death.

A SERIOUS ADVERSE EVENT (SAE) is any AE or suspected adverse reaction occurring at any dose that:

- Results in death.
- Is life-threatening.
- Results in a persistent or significant incapacity or substantial disruption of the ability to conduct normal life functions.
- Requires inpatient hospitalization.
- Prolongs inpatient hospitalization.
- Is a congenital anomaly/birth defect.
- Is a significant medical event (i.e., one that may jeopardize the subject or may require intervention to prevent one or more of the other outcomes listed above).

A **NON-SERIOUS ADVERSE EVENT** is any AE that does not meet the definitions for SAEs as described above.

Each **AE** will be classified as **SERIOUS** or **NON-SERIOUS** using the definitions provided above.

The **SEVERITY** of each AE will be classified as **MILD**, **MODERATE**, **or SEVERE**. The Investigator will review each event and assess its **RELATIONSHIP** to use of investigational product (unrelated, unlikely, possibly, probably, definitely). The AE will be assessed using the following definitions:

Unrelated:

- Event occurring before dosing.
- Event or intercurrent illness due wholly to factors other than investigational product use.

Unlikely:

- Poor temporal relationship with investigational product use.
- Event easily explained by subject's clinical state or other factors.

Possible:

- Reasonable temporal relationship with investigational product use.
- Event could be explained by subject's clinical state or other factors.

Probable:

Reasonable temporal relationship with investigational product use.

- Likely to be known reaction to agent or chemical group, or predicted by known pharmacology.
- Event cannot easily be explained by subject's clinical state or other factors.

Definite:

- Distinct temporal relationship with investigational product use.
- Known reaction to agent or chemical group, or predicted by known pharmacology.
- Event cannot be explained by subject's clinical state or other factors.

8.3. PROCEDURES FOR AE REPORTING BY THE INVESTIGATOR

AEs will be monitored throughout the study and will be recorded on the CRF with the date and time of onset, date and time of resolution, severity, seriousness, causality (relationship to use of investigational product), treatment required, and the outcome.

To elicit AEs, simple questions with minimal suggestions or implications should be used as the initial questions at all evaluation points during the trial. For example:

- How have you felt since your last assessment?
- Have you had any health problems since your last assessment?

The severity of each AE should be categorized as mild, moderate, or severe.

The causality of use of investigational product in relation to the AE will be assessed by the Principal Investigator after careful medical consideration and categorized as unrelated, unlikely, possible, probable, or definite.

If an AE occurs, the Investigator will institute support and/or treat as deemed appropriate. If a non-SAE is unresolved at the time of the last day of the study, an effort will be made to follow up until the AE is resolved or stabilized, the subject is lost to follow-up, or there is some other resolution of the event. The Investigator should make every attempt to follow SAEs to resolution.

8.4. SERIOUS ADVERSE EVENT REPORTING BY THE INVESTIGATOR

Serious Adverse Event Reporting

It is the responsibility of the Investigators or their designees to report any event of this nature to the sponsor or a designee within 24 hours of the event being brought to the Investigators' or their staffs' attention. It is also the responsibility of the Investigator to report all SAEs reported at their site to their Institutional Review Board (IRB), as required. The Investigator should make every attempt to follow all SAEs to resolution.

The following information should be provided when an SAE is reported to the sponsor or designee:

- 1. Protocol Number
- 1. Site Number
- 2. Subject Number
- 3. Subject Demographic information, including:
 - Date of Birth
 - Sex
 - Race
- 4. Investigational product start date
- 5. Date of last dose of investigational product
- 6. Date investigational product reinitiated (if investigational product interrupted)
- 7. SAE information, including:
 - SAE term (diagnosis only; if known or serious signs/symptoms)
 - Description of SAE/narrative
 - Date/time of onset
 - Severity
 - Outcome
 - Date/time of resolution or death (if duration < 24 hours)
 - Relationship to investigational product
 - Action taken with investigational product
- 8. Criteria for classifying the event as serious, including whether the SAE:
 - Resulted in death.
 - Was life-threatening
 - Required inpatient hospitalization.
 - Prolonged inpatient hospitalization.
 - Resulted in a persistent or significant incapacity or substantial disruption of the ability to conduct normal life functions.
 - Was a congenital anomaly/birth defect
 - Important medical events that may not result in death, were not life-threatening, or did not require hospitalization may be considered serious when, based upon appropriate medical judgment, they may jeopardize the patient or subject and may require medical or surgical intervention to prevent one of the outcomes listed in this definition. Examples of such medical events include allergic bronchospasm requiring intensive treatment in an emergency room or at home, blood dyscrasias or convulsions that do not result in inpatient hospitalization, or the development of drug dependency or drug abuse.

- 9. Concomitant medications
- 10. Relevant history
- 11. Possible causes of SAE other than investigational product
- 12. Copy of AE page from the CRF

NOTE: If an SAE occurs in any study involving KPI-121 1.0% ophthalmic suspension that is unexpected and is determined to be related or possibly related to investigational product, all sites will be notified by the sponsor and each site should report it to its IRB.

9. STATISTICS

9.1. STATISTICAL METHODS

Continuous measures (e.g., age) will be summarized descriptively by the mean, standard deviation, median, minimum and maximum values. Categorical measures will be summarized by the number and percent of subjects.

9.1.1. Subject Disposition, Demographic and Background Characteristics

Subject disposition, demographic characteristics, and background variables will be summarized by study group.

9.1.2. Analysis of Efficacy

The primary analysis population will be the Intent-to-Treat (ITT) population, defined as all subjects randomized. A subset of efficacy analyses will be repeated using data from those subjects who were randomized, completed 14 days of study product use, had complete data at Visit 5 (Day 8 ± 1 day) and did not have significant protocol deviations, the Efficacy Evaluable (EE) population. Rescued subjects will be included in the EE population if they did not have significant protocol deviations.

The primary analysis of all ophthalmic efficacy measures will be based on a single study eye for each subject. Each subject's study eye will be defined as the surgery eye. The set of primary endpoints, using hierarchical statistical testing, is (1) proportion of study eyes with complete resolution of anterior chamber cells (grade = 0) at postoperative Visit 5 (Day 8 ± 1 day) maintained through Visit 6 (Day 15 ± 1 day) without receiving rescue medication prior to Visit 6 (Day 15 ± 1 day) as compared between KPI-121 1.0% ophthalmic suspension and placebo, and (2) proportion of study eyes with complete resolution of pain (grade = 0) at postoperative Visit 5 (Day 8 ± 1 day) maintained through Visit 6 (Day 15 ± 1 day) without receiving rescue medication prior to Visit 6 (Day 15 ± 1 day) as compared between KPI-121 1.0% ophthalmic suspension and placebo.

The following scoring scale for anterior chamber cells will be used:

0 = No cells seen

1 = 1 - 5 cells

2 = 6 - 15 cells

3 = 16 - 30 cells

4 =greater than 30 cells

The following scoring scale for ocular pain will be used:

- 0 = None
- 1 = Minimal
- 2 = Mild
- 3 = Moderate
- 4 = Moderately Severe
- 5 = Severe

Using the hierarchical testing scheme, the first test will be the proportion of study eyes with complete resolution of anterior chamber cells (grade = 0) at Visit 5 (Day 8 ± 1 day) maintained through Visit 6 (Day 15 ± 1 day) without receiving rescue medication prior to Visit 6 (Day 15 ± 1 day) as compared between KPI-121 1.0% ophthalmic suspension dosed BID and placebo dosed BID using the χ^2 statistic.

If this test is statistically significant at the two-sided $\alpha = 0.05$ level in favor of the KPI-121 1.0% ophthalmic suspension group, then the difference in the proportion of study eyes with complete resolution of pain (grade = 0) at Visit 5 (Day 8 ± 1 day) maintained through Visit 6 (Day 15 ± 1 day) without receiving rescue medication prior to Visit 6 (Day 15 ± 1 day) as compared between KPI-121 1.0% ophthalmic suspension dosed BID and placebo dosed BID will be tested using the same statistic.

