3.4. DESCRIPTION OF TRIAL DESIGN

This is a Phase 3, multicenter, double-masked, randomized, placebo-controlled, parallel-group study designed to evaluate the safety and efficacy of KPI-121 1.0% ophthalmic suspension versus placebo in subjects who require treatment of postoperative anterior ocular inflammation. Approximately 720 subjects who are candidates for cataract surgery will be screened and approximately 500 subjects who, after undergoing routine, uncomplicated cataract surgery, present at Visit 3 (Day 1) with \geq 2 anterior chamber cells in the study eye will be randomized in this study at approximately 35 centers located in the US.

Subjects who experience postoperative inflammation on the first day following routine, uncomplicated, cataract surgery and who meet all other eligibility criteria will be randomized to one of two study groups in an approximate 1:1 ratio:

- KPI-121 1.0% ophthalmic suspension, BID
- Placebo, BID

Dosing of investigational product will be initiated on the day following surgery, instilled as 1-2 drops in the study eye BID for 14 ± 1 days. The first dose of investigational product will be administered by the subject under the supervision of a designated study team member who is otherwise uninvolved in the assessment or evaluation of the subject. Except for this investigational product administration, no other information or discussion regarding the subject's assigned investigational product will be exchanged, in order to maintain the masking for this trial.

This study will include up to 7 clinic visits (including the surgery day) over 18 to 33 days total study duration. Visit 1 (Screening) will occur between 14 to 1 day(s) prior to surgery and subjects who meet preoperative screening inclusion/exclusion criteria will be entered into the study. At Visit 2 (Surgery/Day 0), subjects will undergo routine cataract surgery according to the Investigator's normal procedures. Visit 3 (Randomization/Day 1) will occur on the day following surgery. Subjects who meet the qualifying postoperative randomization criteria will be eligible for randomization to one of the two study groups and will initiate dosing with investigational product on that day. Following randomization, subjects will be instructed to instill investigational product in the study eye two times a day (BID) for 14 ± 1 days, up until

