5.1.6. Visit 6: End of Investigational Product Use (Day 15 ± 1 day)

The end of investigational product use visit will occur on Day 15 ± 1 day and the following will be performed/assessed (**NOTE:** All ocular assessments must be performed in both eyes.):

- Obtain Subject-Rated Ocular Pain Assessment
- Review use of any concomitant medications since the last visit
- Assess occurrence of any AEs since the last visit
- Collect of used and unused investigational product
- Perform:
 - o UPT
 - o Snellen Distance VA by pinhole method
 - Slit Lamp Biomicroscopy
 - Signs of anterior ocular inflammation (cell and flare grading)
 - Palpebral conjunctival erythema, corneal edema, hyphema, ciliary flush, bulbar conjunctival injection
 - o IOP Measurement
 - Dilated Ophthalmoscopy
- Review dosing compliance.

CONFIDENTIAL

At the end of Visit 6, subjects with inflammation that has not resolved will be treated according to the Investigator's discretion. Regardless of treatment and after cessation of experimental medication, all subjects will be asked to return for follow-up on Days 18 ± 1 day for Visit 7.

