5.4. RESCUE MEDICATION USE

Any subjects not responding adequately to the study medication may be rescued and placed on alternate therapy at the Investigator's discretion at any time. The choice of rescue medication is at the Investigator's discretion. Any subject placed on rescue therapy will discontinue use of the study medication and continue study participation through Visit 7.

Rescued subjects will be considered treatment failures, but the need for rescue therapy will not be considered an AE. Rescued subjects experiencing an AE at the time of rescue will be followed through stabilization or resolution of the AE or the end of the study (whichever comes last). Rescued subjects should not be withdrawn from the study, but rather followed to resolution of signs and symptoms or until the Investigator has deemed the subject is stable.

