9.3. LEVEL OF SIGNIFICANCE

The primary assessment will be evaluated using a 5% level of significance using the hierarchical testing described in Section 9.1.2 Analysis of Efficacy.

All other reported p-values will be considered descriptive and hypothesis generating.

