9.6. SUBJECTS TO BE INCLUDED IN THE ANALYSIS

Efficacy analysis will be performed for all randomized subjects, the Intent-to-Treat (ITT) population. A subset of the efficacy analysis will be repeated using data from those subjects who were randomized, completed 14-days of study product use, had complete data at Visit 5 (Day 8 ± 1 day) and did not have significant protocol deviations, the Efficacy Evaluable (EE) population. Rescued subjects will be included in the EE population if they did not have significant protocol deviations. AEs and other safety parameters will be analyzed for all randomized subjects receiving randomized study product (Safety population).

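### Does the 14-day Efficacy Evaluable rule, which has no tolerance, wrongly exclude compliant subjects with 13 days of dosing?

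*Combined protocol and SAP*

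**What the plan says.** The EE definition appears twice. Section 9.1.2 requires that subjects "completed 14 days of study product use, had complete data at Visit 5" and had no significant protocol deviations. Section 9.6 repeats it with a hyphen: "completed 14-days of study product use, had complete data at Visit 5". Both sections then add an exception: "Rescued subjects will be included in the EE population if they did not have significant protocol deviations".

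Section 3.4 tells subjects to "instill investigational product in the study eye two times a day (BID) for 14 ± 1 days, up until" Visit 6. Section 5.1.6 sets that visit: "The end of investigational product use visit will occur on Day 15 ± 1 day". Dosing starts on Day 1, the day after surgery.

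On rescue, Section 5.4 states: "Any subject placed on rescue therapy will discontinue use of the study medication and continue study participation through Visit 7". It also states: "Rescued subjects will be considered treatment failures".

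The primary analysis population is ITT, all subjects randomized (Section 9.1.2). For p-values outside the primary assessment, Section 9.3 says: "All other reported p-values will be considered descriptive and hypothesis generating".

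**The concern.** Read literally, the EE rule is stricter than the dosing instruction. A subject can follow the protocol exactly, attend Visit 6 on the earliest permitted day, and miss a 14-day threshold. The same sentence gives Visit 5 its ± 1 day window, so the missing tolerance on duration is conspicuous. Nothing says how the Dosing Diary (Appendix 7) is turned into days of use, so two programmers could classify the same subject differently.

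Two further points arise from the same sentences. Rescued subjects stop study product, so those rescued early cannot meet a 14-day condition, and the rescue sentence does not list which conditions it waives. Also, EE asks for complete data at Visit 5 only, while success on the primary endpoints requires grade 0 through Visit 6.

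At stake is whether the EE set reflects adherence or the accident of scheduling. If rescued subjects, all failures, stay in while some compliant unrescued subjects drop out, the loss is not neutral with respect to outcome.

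**Working it through.** **Day count.** Dosing starts on Day 1. Full twice-daily days run from Day 1 to the day before Visit 6. Section 3.4.1 asks for a morning and an evening dose on evaluation days after Visit 3, so a morning dose on the day of Visit 6 is plausible and adds one calendar day.

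| Visit 6 | Full days (doses) | Calendar days with a morning dose (doses) |
|---|---|---|
| Day 14 | 13 (26) | 14 (27) |
| Day 15 | 14 (28) | 15 (29) |
| Day 16 | 15 (30) | 16 (31) |

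Only the Day 14 row is in doubt. It misses 14 on the first count and meets it on the second. The text is therefore ambiguous, and exclusion is not certain.

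**The plan's own figure.** Section 9.2 gives rates of 0.31 and 0.15, 250 per group, two-sided 0.05 and 99% power. With mean rate 0.23,

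z = [0.16·√n − 1.96·√(2·0.23·0.77)] / √(0.31·0.69 + 0.15·0.85).

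At n = 250, z = (2.530 − 1.166)/0.584 = 2.33 and power is 99.0%. The stated figure is reproduced.

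**Random loss from EE.** The documents give no distribution of Visit 6 days, so 10% and 33% per arm are assumptions, starting from 250. The 95% half-width is 1.96·√[(0.31·0.69 + 0.15·0.85)/n].

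| Loss | n per arm | Power | Half-width (points) |
|---|---|---|---|
| 0% | 250 | 99.0% | 7.2 |
| 10% | 225 | 98.3% | 7.6 |
| 33% | 167 | 93.9% | 8.9 |

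**Loss among unrescued subjects only.** Assume rescue in 10% of active and 30% of placebo subjects, and that 20% of unrescued subjects in each arm fall out of EE, with successes lost in proportion.

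- Active: 25 rescued and 225 unrescued. EE = 25 + 0.8·225 = 205. Successes = 0.8·(250·0.31) = 0.8·77.5 = 62. Rate = 62/205 = 30.2%.
- Placebo: 75 rescued and 175 unrescued. EE = 75 + 0.8·175 = 215. Successes = 0.8·(250·0.15) = 0.8·37.5 = 30. Rate = 30/215 = 14.0%.
- The difference is 16.3 points, against 31.0 − 15.0 = 16.0 in the full set.

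**Missing Visit 6 grades.** The design rates imply at least 77.5 active and 37.5 placebo eyes at grade 0 at Visit 5. If 2% to 5% of these had no Visit 6 grade (assumed), that is 1.6 to 3.9 active and 0.8 to 1.9 placebo eyes.

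**The case for a change.** The case for a change is that the contradiction is in the text, not inferred. A nominal intention does not tell a programmer whom to exclude, and a count settled after unmasking is no longer pre-specified. Adding a tolerance and a counting rule would take only a few words and would touch neither dosing nor the primary analysis.

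The wording mismatch stands, and so does the absence of a counting rule. The rest does not carry far:

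- **Nominal usage.** The synopsis and Section 1.2 also write 14 days without a tolerance when they mean the treatment course. Reading the EE condition as completion of that course is natural and agrees with Section 3.4.
- **Rescue.** The rescue sentence only makes sense as an exception. Because rescue stops study product, applying the 14-day condition to rescued subjects would leave the sentence almost without effect.
- **Visit 6 data.** Product is collected and compliance reviewed at Visit 6, so a subject who never attends will mostly be unable to show completed use. A missing Visit 6 grade raises the same question for ITT, so it is not a defect of the EE rule.
- **A fuller redefinition could do harm.** Suppose the Visit 5 data condition were replaced by a requirement that the outcome be determinable. An eye missing Visit 5 would then enter EE if its Visit 6 grade were above 0, but not if it were 0. Membership would depend on outcome, which the present rule avoids.

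**Conclusion.** This is a small gap in wording that analysts would fill sensibly, and no change to the plan follows. The affected group is unrescued subjects whose Visit 6 falls on Day 14, and they are excluded only under one of two reasonable day counts. Ordinary practice is to settle the count and the tolerance when populations are assigned before unmasking, and the protocol's own 14 ± 1 day window supplies the obvious answer.

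Even under the strict reading, the ITT primary analysis, its significance level and its 99% power are untouched. In the supportive EE analysis, power at the design rates stays at 93.9% with an assumed one-third loss. In the illustration of outcome-related loss, each success rate moves by about one point or less and the difference by 0.3 points. These sizes rest on the Section 9.2 rates and on assumed shares of early visits and rescue, since the documents give none. EE p-values fall outside the primary assessment and are descriptive under Section 9.3, so no confirmatory claim hangs on who is in that set.
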